Study Design. The study will be a person-randomized clinical trial comparing the effects of the eCPP tablet-based intervention to an enhanced usual care control condition (Table 1). Parents ($n = 312$) of 2- to 5-year-old children will be recruited from 4 primary care practices and randomly assigned to either the eCPP or control condition. Randomization will occur within sites at the participant level. Intervention parents ($n = 156$) will complete the 6 modules of the eCPP over a period of 3 months (~2 weeks/module; intervention phase) with ongoing access to the program (reference phase) throughout the remainder of the study period. Control condition parents ($n = 156$) will receive tablet-based parenting materials that they would normally receive at their primary care practice (e.g., information regarding nutrition, immunization, and exercise) and have access to the materials over the same intervention time period. Data collection in both conditions will occur at baseline and at 3, 6, and 12 months post-baseline. A descriptive design will be used to evaluate implementation of the eCPP from the perspective of practice sites, clinicians, and parents. Guided by the RE-AIM framework, we will use surveys, electronic health records, data usage metrics, and post-implementation assessments to evaluate the implementation process over the study period.

Measures.

Aim 1: Randomized Control Trial. All measures are written at the 5th grade reading level and administered on an Android tablet as computer assisted, self-interviews (CASIs). An audio option (audio-CASI) is available if parents prefer to listen to the questions. All control and outcome data are obtained by parent self-report and will be collected at each of the 4 data collection time points (baseline, 3, 6, and 12 months post baseline). Previous findings from RCTs of the group-based CPP have found significant findings across three sources of data: parent self-report, teacher report and parent-child observation.^{14,24} In these studies, the parent self-report findings have consistently agreed with other methods of measuring parent and child outcomes. For this reason, the source of parenting and child outcome data for this study will be parent self-report alone.

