We will measure child behavior problems using the Eyberg Child Behavior Inventory (ECBI).⁸¹ The ECBI is a 36-item scale designed to measure the presence and intensity of problem behavior. Each item is measured on two scales: the Problem Scale (dichotomous) and Intensity Scale (7-point). The ECBI is a valid measure of child behavior problems, with established convergent validity across racial and ethnic populations and economically and linguistically diverse samples.⁸¹⁻⁸³ Cronbach's alpha reliabilities of the Intensity and Problem Scale scores are .92 and .99.²⁴ In addition, the Strengths and Difficulties Questionnaire (SDQ) will provide a measure of child behavior problems and prosocial behavior. The 25-item SDQ has a five-factor structure (emotional, conduct, hyperactivity-inattention, peer, and prosocial) using a 3-point scale. Mean Cronbach's alpha for the SDQ is .73.⁸⁴ The SDQ has been validated in multiple cultures and socioeconomic levels.⁸⁵

Aim 2: Cost effectiveness analysis. Data for the cost effectiveness analyses will be drawn from invoices, staff report, study records, EHR, and eCPP electronic time stamps (Table 4). Resources used for the

Table 4. Description of Resource and Cost Measures

Cost Category	Source	Unit of Measure	Translation to Costs
eCPP costs			
eCPP delivery costs	Invoice	Participant	Average cost/participant
Orientation delivery costs			
EHR modification	Programmer report	Minutes/site	Programmer average hourly wage
Clinician time receiving study orientation	Study records	# of clinicians Minutes/clinician	Clinician average hourly wage
Time to lead orientation	Study records	Minutes	Study staff average hourly wage
Clinician costs			
Time to introduce study*	EHR	Minutes/ participant	Clinician average hourly wage
Parent costs			
Time spent learning about the study*	EHR	Minutes/ participant	Parent average hourly wage
Time spent completing eCPP modules	digital time logs	Minutes/ participant	Participant average hourly wage

EHR = Electronic Health Record; *time for introducing and learning about the study includes all parents (non-participants and participants), averaged across the # of participants.

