IMPLEMENTATION: Assessment of the delivery of the introduction of the study by clinicians and associated costs.	Proportion of clinicians that introduce the study to parents of patients aged 2-5 at well-child visits (source: EHR). Tracking and monitoring any implementation adaptations by the clinicians (source: clinicians). NOTE: Evaluation of implementation-related cost will occur as part of data collection and analysis of Aim 2 [Specific Aim 2- cost-effectiveness analysis] .
MAINTENANCE: Evaluation of the practice site maintenance of implementation procedures and participant level maintenance of behavior change.	Evaluation of maintenance of procedures across the study period at the practice sites (source: recruitment rates, # of parents introduced to the study monthly). # of follow-up orientation sessions for clinicians. Assessment of implementation challenges and facilitators, and sustainability of activities in clinical practice (source: post-implementation interviews with clinicians). Maintenance of behavior change over time will be assessed as part of the RCT arm of the study. [Specific Aim 1- RCT (Hypothesis 1b)]

EHR = Electronic Health Record. ^aThe Technology Inventory includes 18 items for parents to respond to about their use and ownership of technology. ^bThe Primary Clinician Survey⁸⁶ is a 25-item measure developed by Metzler and colleagues for their 2014 NIH-funded grant “Parenting Help Online Study” to assess pediatric primary care clinicians’ current practices in helping parents with child behavior problems and parenting concerns. The measure will be used with permission by the authors; no reliability data has been reported. (Appendix B)

Analytic plan.

Aim 1. Test the direct effects of the 6-module eCPP on parenting outcomes (parenting behavior, self-efficacy, and stress) and child outcomes (child problem and prosocial behavior) compared to an enhanced usual care control condition among low-income parents with young children seen in primary care. **HYPOTHESIS 1A:** Relative to parents in the control condition, parents in the eCPP condition will report greater improvements in parenting and child outcomes at the 3-month assessment. **HYPOTHESIS 1B:** The improvements in parenting outcomes and child outcomes the eCPP condition relative to the control condition will be maintained through the 6- and 12-month assessments.

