To determine the effectiveness of the implementation strategy and inform dissemination of the eCPP, a cascaded probability model will be constructed.^{97,98} This will be developed based on the following proportions: (a) the likelihood of clinician adoption at the site [*proportion 1 (pr 1)*], (b) the likelihood of implementation (study introduction) by clinicians at the site [*pr 2*], (c) the likelihood of parent enrollment in the study [*pr 3*], and (d) the likelihood of maintenance of behavior change by the eCPP participants [*pr 4*]. *Pr 4* is defined as the proportion of participants whose parenting and child behavior outcomes are the same or improved at the 12-month data collection compared to the 6-month data collection. The estimated likelihood of parents being introduced to the program will be the product of *pr1* and *pr2*. Second, the compound likelihood of parent enrollment in the study will be the product of *pr1*, *pr2*, and *pr3*. Finally, we will estimate the compound likelihood of maintaining behavior change by examining the product of *pr1*, *pr2*, *pr3*, and *pr4*. This analysis will provide us with two important pieces of information: (1) the probable benefits of the program in terms of how likely it is for parents to achieve maintenance of behavior change and (2) inform us of the phase of the implementation process (as operationalized by *pr1*, *pr2*, *pr3*, and *pr4*) which is likely to interfere with the dissemination of the eCPP.

We will conduct a content analysis of the post-implementation interviews with the clinicians. We will use a coding-based system of content obtained from the interviews using the notes taken during the interview using Atlas.ti software. Atlas.ti allows for the identification, organization, and systematizing of codes that can then be assessed in the context of the clinician interviews. Themes will be summarized by site and used to inform the development of processes and procedures to support the implementation and dissemination of the eCPP in pediatric primary care practice sites.

Bibliography & References Cited

1. Children's Defense Fund. Child poverty in America 2013: State analysis. <http://www.childrensdefense.org/zzz-child-research-data-publications/data/child-poverty-in-america-1.pdf>. Updated 2014. Accessed January 12, 2015.

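### The Aim 3 cascade has no step for parents' use of the self-directed eCPP, so it merges non-use into the maintenance proportion and cannot identify it as a barrier

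*Combined protocol and SAP*

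**What the plan says.** The Analytic plan for Aim 3 builds the cascade from four proportions. The first two concern clinicians: "a) the likelihood of clinician adoption at the site" and "b) the likelihood of implementation (study introduction) by clinicians at the site". The last two concern parents: "c) the likelihood of parent enrollment in the study [*pr 3*], and (d) the likelihood of maintenance of behavior change by the eCPP participants [*pr" (the label that is cut off is pr4). Pr4 is then defined as the share of participants whose outcomes at 12 months are unchanged or better than at 6 months. The definition mentions neither module use nor baseline.

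The plan gives the cascade two purposes. One is to show "the probable benefits of the program in terms of how likely it is for parents to achieve maintenance of behavior change". The other is to find which phase, among those represented by pr1 to pr4, is likely to hold back dissemination.

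Use of the program appears in three other places:

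- Study Design, on the RE-AIM evaluation, says that "we will use surveys, electronic health records, data usage metrics, and post-implementation assessments to evaluate the implementation process over the study period".
- Table 4 lists "Time spent completing eCPP modules" from digital time logs, in minutes per participant, as an input to parent costs.
- The Aim 2 analysis names adherence for the acceptability curves.

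Table 5, which sets out the RE-AIM data, describes Implementation as "Assessment of the delivery of the introduction of the study by clinicians and associated costs". None of its rows lists a measure of parents' use of the modules.

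**The concern.** The eCPP reaches a parent only when that parent opens the modules; Study Design expects all 6 to be done over 3 months. In a self-directed program this step is an obvious place for delivery to fail, and the cascade leaves it out.

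The second purpose is affected most. If non-use lowers pr4, it will be read as a failure to maintain change. If non-users' scores stay flat and pass the pr4 rule, it will not show at all. In neither case can the cascade point to non-use, and a team planning dissemination could spend its effort on the wrong phase.

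The first purpose is affected less directly. A product described as the probable benefit of the program may include parents who had no exposure to it.

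**Working it through.** **Inputs.** The documents give the four factors, the pr4 rule, five outcome domains (parenting behavior, self-efficacy, stress, child behavior problems, prosocial behavior) and an eCPP arm of 156 of 312 parents. They give no value for pr1 to pr4, for any product or for use, so there is no planned figure to reproduce. All values below are assumed for illustration: pr1 = 0.8, pr2 = 0.5, pr3 = 0.3, hence pr1 × pr2 × pr3 = 0.12.

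**Step 1. What pr4 contains.** With u, qU and qN as the share of eCPP parents who use the program and the shares of users and non-users who meet the pr4 rule:

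- Planned: pr4 = u × qU + (1 − u) × qN, and the product is 0.12 × pr4.
- With a use step: the product is 0.12 × u × qU.

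Use has no term of its own in the planned product.

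**Step 2. Behavior as use varies.** Each cell shows the planned product, then the product with a use step.

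| u | qU = qN = 0.6 | qU = 0.7, qN = 0.5 | qU = 0.5, qN = 0.7 |
|---|---|---|---|
| 0 | 0.072 / 0 | 0.060 / 0 | 0.084 / 0 |
| 0.25 | 0.072 / 0.018 | 0.066 / 0.021 | 0.078 / 0.015 |
| 0.50 | 0.072 / 0.036 | 0.072 / 0.042 | 0.072 / 0.030 |
| 0.75 | 0.072 / 0.054 | 0.078 / 0.063 | 0.066 / 0.045 |
| 1 | 0.072 / 0.072 | 0.084 / 0.084 | 0.060 / 0.060 |

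In the first column the planned product does not respond to use. In the third it rises as use falls. At u = 0.5 all three give 0.072. In the first column at u = 0.5, about 156 × 0.5 × 0.6 = 47 non-users are among the 156 × 0.6 = 94 parents counted as maintained.

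If instead qN = 0 and qU = 0.6, the two products agree at every u. At u = 0.5, however, pr4 = 0.5 × 0.6 = 0.30, which would be read as poor maintenance although 60% of users maintained. The number is right, but the phase blamed is wrong.

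**Step 3. Size of the gap.** Planned product ÷ product with a use step = 1 + (1 − u) × qN / (u × qU).

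| qN/qU | u = 0.4 | u = 0.6 | u = 0.8 |
|---|---|---|---|
| 0 | 1.00 | 1.00 | 1.00 |
| 0.5 | 1.75 | 1.33 | 1.13 |
| 1 (ratio = 1/u) | 2.50 | 1.67 | 1.25 |
| 1.4 (0.7/0.5) | 3.10 | 1.93 | 1.35 |

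**Step 4. Can qN be zero under the stated rule?** Take a parent with no true change and normally distributed measurement noise.

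- One continuous outcome: the chance of being no worse at 12 than at 6 months is 0.50.
- One integer score, where ties count as success: the chance is Φ(0.5/SD), or 0.69, 0.60 and 0.54 for an assumed change SD of 1, 2 and 5 points.
- All five outcomes required: 0.5 to the fifth power = 0.03 if independent; by simulation, about 0.10 and 0.20 at assumed correlations of 0.3 and 0.6.

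The plan does not say whether one outcome or all must meet the rule. On either reading qN is above zero.

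**Step 5. The other reading of pr4.** The term eCPP participants is not defined. If it meant users only, pr4 would equal qU, the planned product would be 0.12 × qU, and it would exceed the product with a use step by 1/u whatever qN is. The note to Table 4 contrasts participants with parents who did not join the study, which favors the all-enrolled reading used above.

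**The case against.** Several points on the other side are sound.

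- **The planned product is a legitimate quantity.** With pr4 taken over all eCPP participants, it averages over use and describes how often an enrolled parent meets the rule. Reached, used and maintained is a different quantity. A reader might infer from Step 3 that the planned figure is simply inflated by 1.25 to 2.5. The documents do not support that: those factors need qN = qU, and neither qN/qU nor u is given.
- **Counting non-users comes mainly from the pr4 rule.** A reader might infer that the missing step alone credits the program with parents who never opened a module. It does not. If pr4 captured only maintained change due to the program, qN would be about zero and no non-user would be counted. The counting arises because pr4 compares 12 with 6 months, with no reference to use or baseline.
- **The study does not ignore use.** Usage metrics, module time logs and adherence are all named, so non-use can be described outside the cascade. The public text also lacks some material it refers to, such as Table 1 and a section C.5.a. It would be wrong to say that use goes unmeasured.
- **Aim 3 is descriptive.** No hypothesis test depends on the cascade.
- **Restricting pr4 to completers has its own faults.** It conditions on behavior after randomization and scores a parent who did five of six modules as a failure.

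What these points leave standing is the structural gap. The cascade is the analysis assigned to locate the obstructing phase, and its phases are limited to four that exclude use. The Study Design commitment to usage metrics is not carried into Table 5 or the cascade.

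**Conclusion.** The point holds as a statement about the cascade. Parental non-use cannot emerge from it as the phase that hinders dissemination, because it is merged into pr4. Under the stated pr4 rule, non-users with flat scores can be counted as maintained, though not all will be.

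The numerical effect cannot be fixed from the documents. It is nil if every parent uses the program or if no non-user meets the rule, 1/u if users and non-users meet it equally often, and larger if non-users meet it more often. The loss of diagnostic information does not depend on these values: even where the products agree, low use is read as poor maintenance.

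The change should be made because it lets the cascade answer its own question at little cost. It does not touch the randomized Aim 1 comparison or the Aim 2 cost-effectiveness ratio.

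**What to change.** 1. Between pr3 and pr4, add the proportion of eCPP-assigned parents who used the program, from the electronic time stamps already planned for Aim 2. Define use in advance as any logged module time; take modules completed as a second cut if the logs record it.
2. Report pr4 separately for users and non-users, and state that pr4 over all participants means all eCPP-assigned parents.
3. Show the product with the use step beside the planned all-participant product, so that nothing is lost.
4. Add the usage measure to the Implementation row of Table 5, in line with Study Design.

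Cost: wording in the Aim 3 analysis and Table 5, and a small amount of programming. For the any-use cut no new data are needed. Table 4 gives the unit as minutes per participant, so whether completion can be derived should be confirmed first.

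Downsides: the result depends on the use threshold; pr4 among users is descriptive only, since use is determined after randomization; and the compound likelihood with the use step will be no higher than the planned one.

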intervention include the eCPP costs (e.g., tablet, tech support, and maintenance costs), modification of the EHR, orientation for clinicians, and time for the clinician to introduce the study to parents during well-child visits. Participant costs are primarily the parents' opportunity costs, representing the value of their time spent in the intervention or control condition, respectively. Participant costs include time spent completing the eCPP. Resources used will be translated into costs by multiplying the number of units with the cost per unit for each cost category.

Aim 3: RE-AIM data collection. Process tracking forms will be created to record the evaluation data, if not already part of the RCT outcome data (Table 5). These data will be collected monthly by study staff at each site during the recruitment phase from the 4 primary care practice sites, clinicians, and participants.

Table 5. Data and Source for RE-AIM Evaluation

RE-AIM component	Data and Source
REACH: Proportion and characteristics of parents from the practices that were introduced to and enrolled in the study.	# of monthly well-child visits for children aged 2-5 over course of study recruitment (source: EHR) # of parents who were introduced to the study during a well-child visit (source: EHR) # of parents who enrolled in the study (consented/randomized) # of parents who were not introduced to the study and reason (source: EHR) Characteristics of parents enrolled in the study (source: demographics [C.5.a], Technology Inventory ^a)
EFFICACY: Evaluation of intervention efficacy.	Efficacy of the eCPP intervention is assessed as part of the RCT arm of the study by changes in parenting and child behavior. [Specific Aim 1- RCT (Hypothesis 1a)]
ADOPTION: Characteristics of clinicians and practices oriented and agreeing to deliver the intervention (e.g., introduce the study to eligible parents).	Clinician characteristics: MD or NP, specialty, years in practice, and current practices of managing parenting and child behavior concerns (source: Primary Clinician Survey ^b). Site characteristics: # of patients aged 2-5, average time of well-child visits (source: EHR). # of orientation sessions per practice site and proportion of clinicians that attend the orientation (source: attendance records).

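### The Aim 3 cascade measures consent to a randomized study but is interpreted as program benefit and as barriers to spreading the eCPP, and the listed data cannot separate refusal of research from refusal of the program

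*Combined protocol and SAP*

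**What the plan says.** The Aim 3 part of the Analytic plan builds a cascade from four proportions:

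- pr1: "the likelihood of clinician adoption at the site"
- pr2: "the likelihood of implementation (study introduction) by clinicians at the site"
- pr3: "the likelihood of parent enrollment in the study"
- pr4: "the likelihood of maintenance of behavior change by the eCPP participants", meaning outcomes at 12 months that are no worse than at 6 months

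Table 5 (REACH) supplies the count behind pr3: the number "of parents who enrolled in the study (consented/randomized"). Under Study Design, enrolled parents are randomized, 156 of 312 to control, and assessed at baseline and at 3, 6 and 12 months.

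The wording then moves from study to program. Although pr2 concerns introduction of the study, the plan continues: "The estimated likelihood of parents being introduced to the program will be the product of" pr1 and pr2. The product of all four is said to show "the probable benefits of the program in terms of how likely it is for parents to achieve maintenance of behavior change", and the four factors are to reveal which phase of implementation would impede dissemination of the eCPP.

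On reasons, Table 5 lists the number "of parents who were not introduced to the study and reason (source: EHR"). It lists no reason for parents who were introduced and declined. The post-implementation interviews are with clinicians only.

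**The concern.** A parent can decline enrollment for two different reasons: not wanting the eCPP, or not wanting randomization, a possible control assignment or repeated surveys. Only the first says anything about spreading the program. pr3 merges the two, and the items in Table 5 offer no way to divide them.

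What is at stake is the output that Aim 3 is meant to deliver. If pr3 is the smallest factor, the plan's reading is that parent uptake is the weak link, and effort would go there. If much of the loss is refusal of research, the weaker link may be clinicians introducing the program. The compound likelihood inherits the same ambiguity while being described as benefit.

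**Working it through.** **No figure to reproduce.** The plan gives no value for pr1 to pr4 and no denominator for pr3. Because pr3 is multiplied after pr1 and pr2, I take its denominator to be parents introduced to the study. The check is therefore a comparison of definitions, followed by illustrations in which every input is an assumption.

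**Definitions against interpretation**

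| Term | What is counted | How it is read |
|---|---|---|
| pr1 × pr2 | Introduction to the study, within participating sites | Introduction to the program |
| pr3 | Consent and randomization, both arms | A step toward program benefit |
| pr1 × pr2 × pr3 × pr4 | Study enrollment, then stability from 6 to 12 months among eCPP participants | Probable benefit of the program |

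No sentence in the Aim 3 analysis limits the last reading to study conditions.

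**Illustration 1: can consent change the answer?** Write pr3 = u × c, where u is willingness to use the program and c is willingness to join a randomized study among those parents. Assume pr1 = 0.80, pr2 = 0.60, pr4 = 0.70, so the product is 0.80 × 0.60 × 0.70 × pr3 = 0.336 × pr3.

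| u | c | pr3 | Product | Lowest phase | Product with u in place of pr3 | Lowest phase with u |
|---|---|---|---|---|---|---|
| 0.70 | 0.3 | 0.21 | 0.071 | pr3 | 0.235 | pr2 |
| 0.70 | 0.7 | 0.49 | 0.165 | pr3 | 0.235 | pr2 |
| 0.70 | 0.9 | 0.63 | 0.212 | pr2 | 0.235 | pr2 |
| 0.90 | 0.5 | 0.45 | 0.151 | pr3 | 0.302 | pr2 |
| 0.90 | 0.7 | 0.63 | 0.212 | pr2 | 0.302 | pr2 |
| 0.50 | 0.3 | 0.15 | 0.050 | pr3 | 0.168 | pr3 |
| 0.50 | 0.9 | 0.45 | 0.151 | pr3 | 0.168 | pr3 |

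Consent scales the product in direct proportion. It changes the lowest phase for some inputs. At u = 0.50 it does not, because uptake is lowest either way.

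**Illustration 2: the opposite direction.** Suppose that being in a study raises enrollment to 0.70 when routine uptake would be 0.50. The cascade gives 0.336 × 0.70 = 0.235 against 0.336 × 0.50 = 0.168, too high by a factor of 0.70/0.50 = 1.4. It also names pr2 (0.60) as lowest when uptake (0.50) is lower.

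**Illustration 3: what a decline-reason field would provide.** Assume pr3 = 0.30 and let s be the share of decliners whose reason is research-related. Removing them from the denominator gives pr3 / (1 − (1 − pr3)s):

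- s = 0.2: 0.30 / 0.86 = 0.349
- s = 0.4: 0.30 / 0.72 = 0.417
- s = 0.6: 0.30 / 0.58 = 0.517

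This assumes that parents who object to research would take up the eCPP at the same rate as the rest. If all of them would take it up, the value is pr3 + (1 − pr3)s: 0.44, 0.58 and 0.72. The spread between the two sets shows how much depends on the uptake assumption, so it must be stated with the result.

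**The case against.** Much of the labelling is open. Reach is defined through study enrollment, the product of the first three factors is named as study enrollment, and pr1 and pr2 are both worded as applying at the site. A careful reader who sees a low pr3 is told what it is. The clinician interviews will also inform dissemination. This stands as far as it goes, but the interpretive sentences still speak of program benefit and eCPP dissemination, and clinicians cannot report parents' reasons directly.

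It is also fair that absence from Table 5 shows only that Table 5 omits decline reasons. The tracking forms are still to be created, so a reader who infers that the reasons can never be known goes too far.

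Three further inferences are tempting and not supported:

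- **That the cascade understates program benefit by a known factor.** The inputs have no source in the documents, any factor depends on the uptake assumption, and study features may push enrollment up.
- **That the four practices had agreed beforehand and the product should be scaled down by a practice agreement rate.** The documents name four recruiting practices and refer to practices that agree, but do not say when. Practices declining to host a randomized study would also be declining research, so the scaling would repeat the confusion at another level.
- **That Aim 3 will name the wrong obstacle.** It can; the rows with u = 0.50 show that it need not.

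Finally, repairing pr3 does not turn the product into a measure of benefit. pr3 covers both arms while pr4 covers eCPP participants only, and pr4 counts unchanged outcomes without requiring earlier improvement. This stands, and is why the label has to change as well as the data.

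**Conclusion.** The point holds in a limited form. pr3 is consent to a randomized study, the product and its phases are interpreted as program benefit and program barriers, and the data listed in Table 5 cannot separate the two kinds of refusal. A low pr3 can therefore be misread as a barrier to the eCPP.

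The size and net direction are unknown. The figures above show only that the effect can be large enough to change the phase named as weakest, on assumed inputs. The conclusion rests on the definitions in the text, not on those figures. It concerns the descriptive Aim 3 and leaves the Aim 1 efficacy tests untouched. It is a cheap improvement worth making.

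**What to change.** 1. Add one coded field to the process tracking form: the main reason an introduced parent declined (research-related, program-related, or other/unknown).
2. Report pr3 for all introduced parents, and again excluding research-related declines. State that the second value assumes those parents would take up the eCPP at the same rate as the rest. Carry both through the product as a range.
3. Label the product as study enrollment and maintenance within participating practices, and limit the benefit and dissemination statements to that. The number of practices approached may be reported as description, without entering the product.

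The cost is one field on a form not yet made, one extra line in the results and some rewording. Some decline reasons will be missing or vague, so the two pr3 values mark a range and not a correction. If recruitment has gone ahead without the field, step 3 can still be done in full.
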